10.4.2 Results

A total of 8 scenarios were simulated (two accrual scenarios and four possible ‘truths’ for the clinical benefit rate). The probability of group success for each group is provided for each scenario in the below two tables.

Table 2 provides the probability of group success for each of the cohort – assuming expected accrual of 10 subjects/cohort and 5 subjects/cohort separately

Table 2 – Probability of Group Success**Two-year expected accrual: 10 subjects/cohorts**

Group	Null	Alternative	Two	Half
Lung LSCL	0.158	0.915	0.208	0.305
Bladder	0.131	0.918	0.232	0.322
Breast	0.147	0.909	0.233	0.312
Colorectal	0.138	0.921	0.200	0.276
GIST	0.162	0.921	0.233	0.826
HNSCC	0.139	0.906	0.217	0.834
Ovarian	0.145	0.929	0.786	0.829
Sarcoma	0.135	0.939	0.758	0.852

Two-year expected accrual: 5 subjects/cohorts

Group	Null	Alternative	Two	Half
Lung LSCL	0.132	0.803	0.204	0.258
Bladder	0.140	0.830	0.196	0.265
Breast	0.160	0.807	0.232	0.261
Colorectal	0.135	0.794	0.194	0.278
GIST	0.155	0.826	0.212	0.688
HNSCC	0.140	0.820	0.190	0.657
Ovarian	0.151	0.819	0.587	0.652
Sarcoma	0.139	0.799	0.579	0.667

Entries in normal text represent groups where the treatment effect is 0 (e.g. the treatment is ineffective). Thus, entries in normal text are type I errors. Entries in bold appear where the treatment is effective, and thus indicate the power of the design.

Generally, type I error is controlled below 0.20 under the null scenario (the borrowing compensates for the multiple interim data reviews) and power is an increasing function of the expected sample size (power is higher in the higher accrual situation across treatment rate scenarios). In the alternative scenario there remains decently high probability of success even in the lower accruing situations. When fewer groups are effective in truth, the scenarios “half” and “two” are harder to discern. Note in any particular trial there should be a mix of high and low enrolling groups, thus some groups may enroll closer to 10 subjects while others may only enroll five. This would produce a power value somewhere between the two tables.

Power is reduced and type I error is inflated when the truth is a mixture of effective and ineffective treatment effects across the groups. Generally power is a function of the sample size.

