10.4.5 Supportive analyses

Not applicable.

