14.1.1.1 Primary analysis

We let $Y_{i\cdot}$ be the response indicator for the i th subject, and let R_g be the assumed probability of response within a control population and $\pi_g = \Pr(Y_{i\cdot} = 1 | g_i = g)$ be the underlying probability of response for group g within the trial. We transform to the logit scale for modeling purposes. Let θ_g be the mean log odds treatment effect, i.e.:

$$\theta_g = \log\left(\frac{\pi_g}{1 - \pi_g}\right) - \log\left(\frac{R_g}{1 - R_g}\right).$$

Thus, θ_g is the group specific logistic regression coefficient for group g . The primary analysis is a set of group specific tests that $\theta_g > 0$, meaning that the experimental treatment is better than the assumed control rate for that group. Thus, we wish to test the set of hypotheses

$$H_0: \theta_g \leq 0$$

$$H_1: \theta_g > 0$$

We proceed in a Bayesian fashion, assigning a prior distribution (discussed below) and computing the posterior probability of H_1 within each group g . If, at the final analysis,

$$\Pr(\theta_g > 0 | \text{data}) > 0.80$$

Then group g will be declared a success (thus, the final analysis produces a separate decision for each group). The trial also allows for early stopping of groups, described below.

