14.3.3.3 Final analysis

In addition, recall the final analysis will occur when both accrual and follow-up are complete in all groups, or after the database lock for the primary CSR. If, at the completion of the trial, there is at least 80% probability that the response rate in a group exceeds the historical rate, then the group will be considered a success. Formally:

$$\Pr(\pi_g > R_g) > 0.80.$$

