14.4.4.2 Results

A total of 8 scenarios were simulated (two accrual scenarios and four possible ‘truths’ for the clinical benefit rate). The probability of group success for each group is provided for each scenario in the below two tables.

[Table 14-2](#) provides the probability of group success for each of the cohort – assuming expected accrual of 10 subjects/cohort and 5 subjects/cohort separately

Table 14-2 Probability of group success for each cohort

Two-year expected accrual: 10 subjects/cohort				
Group	Null	Alternative	Two	Half
Lung LSCL	0.158	0.915	0.208	0.305
Bladder	0.131	0.918	0.232	0.322
Breast	0.147	0.909	0.233	0.312
Colorectal	0.138	0.921	0.200	0.276
GIST	0.162	0.921	0.233	0.826
HNSCC	0.139	0.906	0.217	0.834
Ovarian	0.145	0.929	0.786	0.829
Sarcoma	0.135	0.939	0.758	0.852
Two-year expected accrual: 5 subjects/cohort				
Group	Null	Alternative	Two	Half
Lung LSCL	0.132	0.803	0.204	0.258
Bladder	0.140	0.830	0.196	0.265
Breast	0.160	0.807	0.232	0.261
Colorectal	0.135	0.794	0.194	0.278
GIST	0.155	0.826	0.212	0.688
HNSCC	0.140	0.820	0.190	0.657
Ovarian	0.151	0.819	0.587	0.652
Sarcoma	0.139	0.799	0.579	0.667

Entries in red represent groups where the treatment effect is 0 (e.g. the treatment is ineffective). Thus, entries in red are type I errors. Entries in green appear where the treatment is effective, and thus indicate the power of the design.

Generally, type I error is controlled below 0.20 under the null scenario (the borrowing compensates for the multiple interim data reviews) and power is an increasing function of the expected sample size (power is higher in the higher accrual situation across treatment rate scenarios). In the alternative scenario there remains decently high probability of success even in the lower accruing situations. When fewer groups are effective in truth, the scenarios “half” and “two” are harder to discern. Note in any particular trial there should be a mix of high and low enrolling groups, thus some groups may enroll closer to 10 subjects while others may only enroll five. This would produce a power value somewhere between the two tables.

Power is reduced and type I error is inflated when the truth is a mixture of effective and ineffective treatment effects across the groups. Generally power is a function of the sample size.

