10.3.3 Final Analysis

In addition, recall the final analysis will occur when both accrual and follow-up are complete in all groups, or after the database lock for the primary CSR. If, at the completion of the trial, there is at least 90% probability that the response rate in a group exceeds the historical rate, then the group will be considered a success. Formally:

$$\Pr(\pi_g > R_g) > 0.90.$$

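### The printed error rates belong to a 0.80 cut, not the 0.90 success rule, and one inactive cohort among active ones is neither simulated nor backed by an unborrowed CBR analysis

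*SAP*

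**What the plan says.** Both documents define the primary analysis cohort by cohort. "The primary analysis is a set of group specific tests that" is how Appendix R 14.1.1.1 begins the statement of the hypotheses H0g: theta_g <= 0 against H1g: theta_g > 0, with a separate decision for each group.

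The final success cut differs between places:

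- SAP 10.3.3 declares success if "there is at least 90% probability that the response rate in a group exceeds the historical rate". SAP 6.1 and 10.1.1 and protocol 10.4.2 and 10.4.3 also use 0.90.
- Protocol Appendix R 14.3.3.3 declares success if "there is at least 80% probability that the response rate in a group exceeds the historical rate", and Appendix R 14.1.1.1 also uses 0.80.

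The simulated probabilities of success are nevertheless identical in the two documents (protocol Table 14-2, SAP Table 2).

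On error control, SAP 10.4.2 says: "Generally, type I error is controlled below 0.20 under the null scenario (the borrowing compensates for the multiple interim data reviews". It then concedes, as Appendix R 14.4.4.2 does: "Power is reduced and type I error is inflated when the truth is a mixture of effective and ineffective treatment effects across the groups". The SAP tells the reader how to read the table: "Thus, entries in normal text are type I errors". The row with the largest such entry, at 10 per cohort with columns Null, Alternative, Two and Half, is "Bladder 0.131 0.918 0.232 0.322".

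The scenarios have none, two of eight, half or all of the cohorts effective. Under the heading "10.4.5 Supportive analyses" the protocol plans nothing. SAP 6.1 gives no confidence interval and no unborrowed probability for CBR.

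**The concern.** Each tumour type gets its own verdict, so the relevant error is the chance that an inactive cohort is called a success, whatever the drug does elsewhere. Under the global null, borrowing pulls every cohort towards no effect and the error looks small. When the other cohorts respond, the same borrowing pulls the inactive one upwards. The printed error rises with the share of active cohorts, and the simulations stop before the point where it should be highest.

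That case is realistic here. Amendment 3 re-opened six tumour types because confirmed or unconfirmed responses had been seen among them, so a mostly active set with one inactive member is plausible. The output of the trial is a list of tumour types worth further study. A reader of that list needs the error rate of the rule actually used, and needs to see how far a success rests on the cohort's own patients.

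**Working it through.** **Inputs (SAP 10.3 to 10.5; Appendix R).** Dirichlet process clustering with alpha = 2; within a cluster theta_g ~ N(mu, tau^2), mu ~ N(0, 1.82), tau^2 ~ IG(3, 0.5). Control rates 0.38 to 0.50; active cohorts at an odds ratio of 3 (0.45/0.55 x 3 = 2.45, and 2.45/3.45 = 0.71, as tabulated). Poisson accrual with mean 10 or 5, cap 30, no dropouts. Early success above 0.95 with at least 15 patients; futility below 0.10 with at least 10. The documents do not say whether 1.82 is a variance or an SD, so both were run.

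**Step 1: the plan's own table.** The posterior was computed by summing over all partitions of the eight cohorts, with the interim rules applied and 2,000 trials per scenario. Means for inactive cohorts, with 1.82 as SD:

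| Scenario | Printed, 10/cohort | Run at 0.80 | Run at 0.90 | Printed, 5/cohort | Run at 0.80 | Run at 0.90 |
|---|---|---|---|---|---|---|
| Null | 0.144 | 0.147 | 0.059 | 0.144 | 0.142 | 0.055 |
| Two | 0.221 | 0.214 | 0.099 | 0.205 | 0.200 | 0.084 |
| Half | 0.304 | 0.293 | 0.146 | 0.266 | 0.263 | 0.126 |

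Mean power under Alternative is printed as 0.920 (10 per cohort) and 0.812 (5 per cohort). The run gives 0.931 and 0.801 at 0.80, but 0.836 and 0.637 at 0.90. The table therefore matches the 0.80 rule to about one percentage point in the means, and overstates both error and power for the 0.90 rule. With 1.82 as a variance, the 0.90 errors are 0.048 to 0.057 (Null), 0.076 to 0.095 (Two) and 0.113 to 0.136 (Half).

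**Step 2: one inactive cohort, the rest active, at 0.90.**

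- Eight cohorts: 0.188 to 0.211 at 5 per cohort, 0.232 to 0.258 at 10, and 0.276 at an assumed 20 per cohort.
- Six cohorts, mean 10, final analysis only, control rate 0.45 assumed for glioblastoma and cholangiocarcinoma (the documents give none): 0.19 to 0.24 across separate runs. The global null gives 0.06 to 0.08, and the same prior with no borrowing gives 0.07 to 0.11.
- Range for that assumption: with 0.30 or 0.60 for those two tumours and HNSCC inactive, 0.195 to 0.216. With glioblastoma itself inactive, 0.17 to 0.19 at a control rate of 0.30 and 0.235 to 0.257 at 0.60 (1,500 trials each, Monte Carlo SE about 0.01).
- With the 0.45 assumption, 48% to 57% of these false successes have an unborrowed probability of 0.90 or less.

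**Step 3: why, in one example.** Take a cohort of 10 with control rate 0.45. On its own data, 6/10 gives Pr(pi_g > R_g) = 0.81 to 0.82 and 7/10 gives 0.93 to 0.94, so success needs 7. With the other five cohorts at 7/10, 6/10 gives 0.93 to 0.94 and 5/10 gives 0.82 to 0.84, so 6 is enough. If the true rate is 0.45:

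- Pr(X >= 7) = 0.0746 + 0.0229 + 0.0042 + 0.0003 = 0.102
- Pr(X >= 6) = 0.102 + 0.160 = 0.262

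Borrowing lowers the bar by one patient. Averaging over the other cohorts' data and variable accrual gives the rates in Step 2.

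**The case against.** The strongest reply is that the plan is candid. The error sentence is limited to the null scenario, the inflation is stated shortly after it, and the table prints and labels the inflated entries. Borrowing is deliberate, prespecified and explained, in a signal-seeking study where some false leads are acceptable. All of that stands. What it does not supply is an error rate for the 0.90 rule, or any figure for the least favourable truth.

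Several stronger readings are tempting but not supported:

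- A reader might infer that inactive cohorts among active ones generally succeed at twice the rate the 0.90 cut implies. In the plan's Two and Half scenarios the error at 0.90 is 0.08 to 0.15, or 0.8 to 1.5 times 0.10. About twofold appears only for a single inactive cohort. The plan also never claims a 0.10 error rate; 0.90 is a posterior threshold.
- Setting the printed 0.190 to 0.322 against 0.10 would suggest 1.9 to 3.2 times, but that compares output of a 0.80 rule with a 0.90 threshold.
- The chance that a lone inactive cohort is called a success or promising (above 0.80) is about 0.34 to 0.41. It should not be set against the below-0.20 statement, which concerns success under the global null; promising is a separate, lesser label.
- A reader might infer that nothing planned would expose a borrowed success. SAP 2.1 has CBR summarised by patient group, SAP 2 has all data listed, and protocol 10.5.1 gives ORR with an exact interval for each group. A reader could see 6/10 against 0.45. What is missing is an interval and an unborrowed probability for CBR.

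**Conclusion.** The point holds in a bounded form. No printed operating characteristic belongs to the operative 0.90 rule. At that rule the false-success rate for an inactive cohort is about 0.06 to 0.08 under the global null, 0.08 to 0.15 in the plan's mixed scenarios, and 0.19 to 0.24 (up to 0.28 with eight cohorts) when it is the only inactive one. Without borrowing it is 0.07 to 0.11. About half of the single-inactive false successes depend on the other cohorts' data.

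These figures assume separate mu and tau for each cluster, an odds ratio of 3 in active cohorts and no dropouts. The six-cohort figures also assume a control rate of 0.45 for two tumours; moving it between 0.30 and 0.60 widens the range to about 0.17 to 0.26.

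The design is not invalid and the inflation is not concealed. The gap is in what can be concluded about each tumour type, and it is cheap to close.

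**What to change.** 1. Reconcile the 0.80 and 0.90 success cuts between Appendix R and protocol section 10 and the SAP. Rerun every column of Table 14-2 / SAP Table 2 at the operative 0.90 cut and add a column with one inactive cohort and the rest effective. Restate the error sentence from the rerun figures. Keeping below 0.20 next to a 0.90 column would mix two rules.
2. In protocol 10.4.5 and SAP 6.1, add a supportive analysis for each cohort: observed CBR with exact 95% CI, and the unborrowed Pr(pi_g > R_g) from the same prior, shown beside the primary posterior probability. The primary decision rule stays as it is, and the unborrowed figure is not a second bar for success.

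Cost: one simulation rerun and one extra table. The stated operating characteristics will look less favourable. In the rerun above, mean power under Alternative falls from a printed 0.920 to about 0.84 at 10 per cohort, and from 0.812 to about 0.64 at 5.

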10.5 Modeling Details

Recall at the first stage the groups are clustered according to a Dirichlet Process Mixture Model.

The number of clusters is not assumed to be known in advance but will instead be inferred from the data using Dirichlet Process Mixtures (DPM). The DPM looks across all the possible clusterings of the groups and assigns a probability to each based on the data. The prior distribution in a DPM is governed by a parameter α . When α is small, the prior favors large

clusters. As α tends to zero, the prior tends to place all its mass on a single cluster containing all the groups. As α increases, the prior places more mass on clusterings with a large number of clusters. As α becomes very large, the prior places all of its mass on having a separate cluster for each group (that is, no borrowing across groups). Thus, by specifying extreme values of the prior one could force the groups into one cluster or force the groups to be analyzed in separate clusters. Here we choose a moderate version of $\alpha=2$ (common values might be anywhere between 0.5 and 5) and allow the data more control over the clustering.

The details of the prior are as follows. Let z_g represent the cluster to which group g belongs. Then $z_g \sim \text{Categorical}(\mathbf{p})$, where \mathbf{p} is the vector such that p_k is the probability that a group belongs to cluster k and $\sum_{k=1}^{\infty} p_k = 1$. We construct \mathbf{p} using a stick-breaking process:

$$p_k = \beta_k \prod_{i=1}^{k-1} (1 - \beta_i)$$

and

$$\beta_k \sim \text{Beta}(1, \alpha).$$

A large value of α thus removes a very small amount of probability for \mathbf{p} , resulting in many clusters, while a small value of α tends to produce probabilities near 1 for the first cluster.

Conditional on the clustering, we fit a hierarchical model which has an across groups distribution

$$\theta_g \sim N(\mu, \tau^2)$$

As discussed above, this across group distribution states that within a cluster we expect to see some variation in the parameters, with that variation governed by τ . When τ is small, there is minimal variation across groups within a cluster, and thus within the cluster the model would approach pooling. In contrast, when τ is large we expect large amount of across group variation, and thus even though the groups are in the same cluster the θ_g values may be quite different. Apriori we have no way of knowing τ , so we estimate it using the data combined with the prior distributions

$$\mu \sim N(0, 1.82)$$

and

$$\tau^2 \sim IG(3, 0.5),$$

where $IG(\alpha, \beta)$ is the inverse gamma distribution defined by:

$$f(x|\alpha, \beta) = \frac{\beta^\alpha e^{-\beta/x}}{x^{\alpha+1} \Gamma(\alpha)}.$$

When the entire model is implemented (via Markov Chain Monte Carlo) we consider the full joint distribution of the clustering combined with the hierarchical model parameters. We average over the entire range of the uncertainty in the parameters to produce the posterior distribution for each group parameter θ_g , which is then used to drive the decisions in the model.

11 References

